7.3.5 Immunologic Assessments

7.3.5.1 Primary Assessments

- Donor specific antibody testing at Month 6
- Cell surface cytokine secretion in response to donor cell antigen by direct and indirect stimulation at Month 6

- Cell surface cytokine secretion in response to CMV and EBV antigens by direct and indirect stimulation at Month 6
- Immunophenotyping to determine overall immune profile at Month 6

7.3.5.2 Secondary Assessments

- Donor specific antibody testing at Months 1 and 3, and month 12 if electing to continue in study
- Cell surface cytokine secretion in response to donor cell antigen by direct and indirect stimulation at Months 1 and 3, and month 12 if electing to continue in study
- Cell surface cytokine secretion in response to CMV and EBV antigens by direct and indirect stimulation at Months 1 and 3, and month 12 if electing to continue in study

#### 7.3.5.3 Brief summary of methods immunologic assessment

Cell surface cytokine secretion will be performed using both alloantigen and viral antigen stimuli following our previously published protocol [7]. Cells previously banked from kidney transplant donors will be used to analyze allospecific cells for the presence of both direct and indirect immune response. A cocktail of fluorescent conjugated monoclonal antibodies against cell surface markers and secreted cytokines will be used to distinguish between alloreactive naïve versus memory T cells using multiparameter flow cytometry. Results will be expressed as percentage of cells expressing either IFN- $\gamma$  or IL-10 per each of the various lymphocytes subsets.

Analysis of virus-specific cytokine secretion will be performed in a similar fashion for analysis of indirect immune response to virus. PBMCs will be incubated with commercially available overlapping peptide pools for major CMV and EBV antigens and incubated in the presence of anti-CD28 antibody.

Immunophenotyping will be performed to further dissect the influence of belatacept on the immune response. PBMCs at each time point will be assessed by multiparameter flow cytometry using panels aimed at characterization of T cell immunophenotypes including central memory, effector memory, and naïve cells, activated cells, B cells, NK cells, and T regulatory cells.

See also section 3.1.3 above for table of antibody panels to be used and justification of approach.

7.3.6 Potential for premature termination of clinical trial

The incidence of acute rejection during the first year post-transplant is typically about 10% for a cyclosporine based immunosuppression regimen [4]. If a two-fold or greater (>=20%) incidence of acute rejection is observed, the patient demographics and data collected will be reviewed and the trial will be considered for premature termination. Because of the small

number of patients participating in this trial, an up to two-fold deviation from expected rates was established.

8 Drug Product

8.1 Study Product Bristol-Myers Squibb will supply Belatacept.:

#### Identification

Belatacept is supplied as a sterile, white or off-white lyophilized powder for intravenous administration. Prior to use, the lyophile is reconstituted with a suitable fluid to obtain a clear to slightly opalescent, colorless to pale yellow solution, with a pH in the range of 7.2 to 7.8. Each 250 mg single-use vial of belatacept also contains: monobasic sodium phosphate (34.5 mg), sodium chloride (5.8 mg), and sucrose (500 mg).

8.2 Packaging and Labeling

Belatacept for Injection will be supplied in a 250 mg/vial, and is administered by IV injection.

#### Belatacept for Injection, 250 mg/Vial

Belatacept for Injection, 250 mg/Vial, is a sterile non-pyrogenic lyophilized powder. Each vial contains 275 mg of belatacept, 550 mg of sucrose, 38.0 mg of sodium phosphate monobasic monohydrate, 6.4 mg of sodium chloride, and 1 N sodium hydroxide/1 N hydrochloric acid solution sufficient to adjust pH to 7.5. A 10% overfill is included in each vial to account for VNS holdup.

8.3.1 Drug Product Preparation Belatacept :

A pharmacist or qualified personnel at the site, not otherwise associated with the conduct of the study, will reconstitute the drug for i.v. administration.

Care must be taken to assure sterility of the prepared solution, as the drug product does NOT contain any antimicrobial preservatives or bacteriostatic agents.

Recommended safety measures for preparation and handling include protective clothing, gloves, and safety cabinets. Unused drug product solution should be discarded as per the site procedures. Constituted solutions of belatacept may foam; therefore, shaking should be avoided. Error! Bookmark not defined,

**Deleted:** 

Belatacept is provided as a lyophilized powder in preservative-free, single-use vials. Each vial provides 250 mg of belatacept for intravenous administration. Each vial must be reconstituted with 10.5 mL of a suitable reconstitution fluid, **using a silicone-free syringe**.

Suitable fluids for reconstitution include sterile water for injection, 0.9% sodium chloride injection or 5% dextrose injection. The reconstituted solution must be further diluted with either 0.9% sodium chloride injection or 5% dextrose injection to belatacept concentrations between 2 mg/mL and 10 mg/mL, before administration by intravenous infusion. The diluted reconstituted solution must be administered as an intravenous (IV) infusion at a relatively constant rate over 30 minutes.

Prior to administration, the belatacept infusion solution should be inspected visually for particulate matter or discoloration, and the solution should be discarded if any particulate matter or discoloration is observed. The entire, fully diluted belatacept infusion should be administered over a period of 30 minutes and must be administered with an infusion set and a sterile, non-pyrogenic, low protein binding filter (pore size of 0.2  $\mu$ m to 1.2  $\mu$ m). Following administration, it is recommended that the intravenous line be flushed with infusion fluid to ensure administration of the complete dose Any unused portion of the infusion solution should not be stored for reuse.

Other medicines: belatacept should not be infused concomitantly in the same intravenous line with other agents. The investigational product should be stored in a secure area according to local regulations. The investigator is responsible for ensuring that it is dispensed only to study subjects and only from official study sites by authorized personnel, as dictated by local regulations.

See Section 6.2.2 for additional details on study medication administration.

No data are available on the compatibility of Belatacept with other i.v. substances. Other drug substances should not be added or infused simultaneously through the same

i.v. line. Assure adequate, appropriate flushing between each drug substance if multiple drugs are administered through the same line sequentially. Other protocol-required drug products:

Other protocol-required drug products should be administered to subjects according to the dosing details provided in Section 6.2.6.

#### 8.3.2 Recommended Storage Conditions

The investigator is responsible for ensuring that the product is stored under the appropriate environmental conditions (temperature, light, and humidity), and will be stored and reconstituted as per the belatacept (Nulojix) package insert.

#### 8.4 Drug Product Records at Site

It is the responsibility of the investigator to ensure that a current record of drug product disposition is maintained at each study site where drug product is inventoried and disposed.

Records or logs must comply with applicable regulations and guidelines, and should include:

- Amount received and placed in storage area
- Amount currently in storage area
- Label identification number or batch number and use data or expiry date
- Dates and initials of person responsible for each drug product inventory entry/movement
- Amount dispensed to each subject, including unique subject identifiers
- Non-study disposition (e.g., lost, wasted, broken)

8.5 Return and Destruction of Investigational Product Not applicable

8.6 Retained Samples for Bioavailability/Bioequivalence Studies Not applicable.

#### 9 ADVERSE EVENT REPORTING IN CLINICAL TRIALS

#### 9.1 Importance of Adverse Event Reporting

Timely and complete reporting of safety information assists BMS in identifying any untoward medical occurrence, thereby allowing: (1) protection of the safety of study subjects; (2) a greater understanding of the overall safety profile of the drug product; (3) recognition of dose-related toxicity; (4) appropriate modification of study protocols; (5) improvements in study design or procedures; and (6) adherence to worldwide regulatory requirements.

#### 9.2 Collection of Safety Information

An *Adverse Event (AE)* is defined as any new untoward medical occurrence or worsening of a pre-existing medical condition in a patient or clinical investigation subject administered an investigational (medicinal) product and that does not necessarily have a causal relationship with this treatment. An AE can therefore be any unfavorable and unintended sign (including an abnormal laboratory finding, for example), symptom, or disease temporally associated with the use of investigational product, whether or not considered related to the investigational product.

Adverse events can be spontaneously reported or elicited during open-ended questioning, examination, or evaluation of a subject. (In order to prevent reporting bias, subjects should not be questioned regarding the specific occurrence of one or more AEs.)

A *Serious Adverse Event (SAE)* is any untoward medical occurrence that at any dose:

results in death

- is life-threatening (defined as an event in which the subject was at risk of death at the time of the event; it does not refer to an event which hypothetically might have caused death if it were more severe)
- requires inpatient hospitalization or causes prolongation of existing hospitalization (see note below for exceptions)
- results in persistent or significant disability/incapacity
- is a congenital anomaly/birth defect

is an important medical event, defined as a medical event that may not be immediately life-threatening or result in death or hospitalization but, based on appropriate medical and scientific judgment, may jeopardize the subject or may require intervention (e.g., medical, surgical) to prevent one of the other serious outcomes listed above. Examples of such events include but are not limited to intensive treatment in an emergency department or at home for allergic bronchospasm; blood dyscrasias or convulsions that do not result in hospitalization. Potential drug induced liver injury (DILI) us also considered an important medical event (see Section 7.6 for the definition of potential DILI.

Suspected transmission of an infectious agent (e.g., any organism, virus or infectious particle, pathogenic or non-pathogenic) via the study drug is an SAE.

Although pregnancy, overdose and cancer are not always serious by regulatory definition, these events must be handled as SAEs (See Section 7.5 for reporting pregnancies).

**NOTE:** The following hospitalizations are not considered SAEs:

- a visit to the emergency room or other hospital department lasting less than 24 hours that does not result in admission (unless considered an "important medical event" or a life-threatening event)
- elective surgery planned before signing consent
- admissions as per protocol for a planned medical/surgical procedure
- routine health assessment requiring admission for baseline/trending of health status (e.g., routine colonoscopy)
- medical/surgical admission for purpose other than remedying ill health state that was planned before study entry. Appropriate documentation is required in these cases.
- admission encountered for another life circumstance that carries no bearing on health status and requires no medical/surgical intervention (e.g., lack of housing, economic inadequacy, caregiver respite, family circumstances, administrative).

Adverse events can be spontaneously reported or elicited during open-ended questioning, examination, or evaluation of a subject. To prevent reporting bias, subjects should not be questioned regarding the specific occurrence of one or more adverse events.

If known, the diagnosis of the underlying illness or disorder should be recorded, rather than its individual symptoms. The following information should be captured for all AEs: onset, duration, intensity, seriousness, relationship to investigational product, action taken, and treatment required. If treatment for the event was administered, it should be recorded in the medical record. The investigator must supply BMS and the IRB/IEC with any additional information requested, notably for reported deaths of subjects.

All SAEs, whether related or unrelated to belatacept, and all pregnancies must be reported to BMS (by the investigator or designee) within 24 hours.

All SAEs should be reported via confirmed facsimile (fax) transmission, or scanned and reported via electronic mail to:

SAE Email Address: [contact]

SAE Fax Number: <<[contact]>>

For studies conducted under an **Investigator IND**, any event that is both serious and unexpected must be reported to the Food and Drug Administration (FDA) as soon as possible **and no later than 7 days** (for a death or life-threatening event) **or 15 days** (for all other SAEs) **after the investigator's or institution's initial receipt of the information.** BMS will be provided with a simultaneous copy of all adverse events filed with the FDA. SAEs should be reported on MedWatch Form 3500A, which can be accessed at: http://www.accessdata.fda.gov/scripts/medwatch/.

#### MedWatch SAE forms should be sent to the FDA at:

MEDWATCH [name] Fax: [name] ([name]) http://www.accessdata.fda.gov/scripts/medwatch/

All SAEs should simultaneously be faxed or e-mailed to BMS at:

Global Pharmacovigilance & Epidemiology Bristol-Myers Squibb Company [contact] Email: [contact]

If an ongoing SAE changes in its intensity or relationship to study drug or if new information becomes available, a follow-up SAE report should be sent within 24 hours to the BMS using the same procedure used for transmitting the initial SAE report. All SAEs should be followed to resolution or stabilization.

The collection of non-serious adverse event (NSAE) information should begin at initiation of study drug. NSAE information should also be collected from the start of a placebo lead-in period or other observational period intended to establish a baseline status for the subjects. NSAEs should be followed to resolution or stabilization, or reported as SAEs if they become

serious. Follow-up is also required for NSAEs that cause interruption or discontinuation of study drug, or those that are present at the end of study treatment as appropriate. All identified NSAEs must be documented appropriately.

9.3 Potential Drug-Induced Liver Injury (DILI)

Wherever possible, timely confirmation of initial liver-related laboratory abnormalities should occur prior to the reporting of a potential DILI event. All occurrences of potential DILIs, meeting the defined criteria, must be reported as SAEs (see Section 7.2.1 for reporting details).

Potential drug induced liver injury is defined as

1. AT (ALT or AST) elevation > 3 times upper limit of normal (ULN)

AND

2. Total bilirubin > 2 times ULN, without initial findings of cholestasis (elevated serum alkaline phosphatase),

AND

3. No other immediately apparent possible causes of AT elevation and hyperbilirubinemia, including, but not limited to, viral hepatitis, pre-existing chronic or acute liver disease, or the administration of other drug(s) known to be hepatotoxic.

#### 9.4 Adverse Events Related to Study Conditions

If the investigator believes that an SAE is not related to the drug product, but is potentially related to the conditions of the study, (such as withdrawal of previous therapy, or complication of a trial procedure), the relationship should be specified in the narrative section of the SAE page of the CRF.

9.5 Laboratory Test Abnormalities

All laboratory test values captured as part of the study should be recorded on the appropriate laboratory test results pages of the CRF, or be submitted electronically from a central laboratory. In addition, in order for BMS to collect additional information about clinically important laboratory abnormalities, at a minimum, the following laboratory abnormalities should be captured on the AE or SAE pages of the CRF as appropriate:

• Any laboratory test result that meets the criteria for a SAE

• Any laboratory abnormality that required the subject to have drug product discontinued or interrupted

• Any laboratory abnormality that required the subject to receive specific corrective therapy.

It is expected that wherever possible, the clinical, rather than the laboratory term would be used by the reporting investigator (e.g., 'anemia' vs. 'low hemoglobin value').

9.6 Other Safety Considerations

Any clinically significant changes noted during interim or final physical examinations, ECGs, x-rays, and any other potential safety assessments, whether or not these procedures are required by the protocol, should also be recorded on the appropriate AE page of the CRF (i.e., non-serious or serious).

#### 9.7 Pregnancy

Sexually-active WOCBP must use an effective method of birth control during the course of the study, in a manner such that risk of failure is minimized. (See Section 5.1 for definition of WOCBP).

#### Precautions

WOCBP should be advised against becoming pregnant from the beginning of the study until 8 weeks or 5 half lives (whichever is greater) after administration of the last dose.

Subjects should be instructed to contact the Investigator immediately if pregnancy is suspected (e.g., missed or late menstrual period). Male subjects should be advised to avoid unprotected sex throughout the study and until sperm produced during the period of drug exposure has been cleared. Drug-exposed sperm may be present in the semen for 3 months following the passage of 5 half lives of the study drug.

Subjects should be advised to notify the Investigator of any change in birth control method during exposure to Study Drug or if they need to take any prescription drug or other medication not prescribed by the Investigator. The Investigator should be aware of changes in birth control method so that the use of a study-prohibited contraceptive method is identified.

Hormonal contraceptives could be depressed from drug-drug interactions with the study drug or other concomitant medications. Hormonal contraceptives should not be used to prevent pregnancy until a Drug-Drug Interaction (DDI) study has verified that the pharmacokinetics of the hormone contraception remain at therapeutic levels, and this can be substantiated by appropriate PK studies and the investigator believes that this is appropriate for the subject.

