#### 2.2 Secondary Objectives

Secondary Outcome Measures:

- Donor specific antibody testing at Months 1 and 3 (and month 12 if continuing in study)
- Cell surface cytokine secretion in response to donor cell antigen by direct and indirect stimulation at Months 1 and 3 (and month 12 if continuing in study)
- Cell surface cytokine secretion in response to CMV and EBV antigens by direct and indirect stimulation at Months 1 and 3 (and month 12 if continuing in study)

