#### Age and Gender

4) Men and women, ages 18 and older, inclusive

5) Women of childbearing potential (WOCBP) must be using an adequate method of contraception to avoid pregnancy throughout the study and for up to 8 weeks after the study in such a manner that the risk of pregnancy is minimized. See section 9.7 below for details regarding handling of WOCBP subjects.

WOCBP includes any female who has experienced menarche and who has not undergone successful surgical sterilization (hysterectomy, bilateral tubal ligation, or bilateral oophorectomy) or is not postmenopausal (defined as amenorrhea  $\geq 12$  consecutive months; or women on hormone replacement therapy with documented serum follicle stimulating hormone level > 35 mIU/mL). Even women who are using oral, implanted, or injectable contraceptive hormones or mechanical products such as an intrauterine device or barrier methods (diaphragm, condoms, spermicides) to prevent pregnancy or practicing abstinence or where the partner is sterile (e.g., vasectomy), should be considered to be of child bearing potential. WOCBP who are taking MMF must in addition use methods of birth control as stipulated in the package insert, namely:

Either intrauterine device, or partner with vasectomy, or one hormone (oral contraceptive pill, transdermal patch, vaginal ring, or progesterone injection or implant) and one barrier method (diaphragm or cervical cap with spermicide, contraceptive sponge, or male or female condom), or two barrier methods as described above.

WOCBP must have a negative serum pregnancy test (minimum sensitivity 25 IU/L or equivalent units of human chorionic gonadotropin [HCG]) within 72 hours prior to the start of study medication then every 3 months during the period of study participation.

6) Men must use an adequate method of contraception throughout the study, and for up to 8 weeks after the last infusion, so that the risk of pregnancy to their partners is minimized.

7) MMF must be dosed at 500 mg by mouth twice daily or greater at the time of study entry

8) Prednisone must be dosed at >=10 mg by mouth daily for patients less than 6 weeks posttransplantation, and at >=5mg by mouth daily for patients greater than 6 weeks posttransplantation at the time of study entry.

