5.2 Exclusion Criteria Gender and Reproductive Status

1) WOCBP who are unwilling or unable to use an acceptable method to avoid pregnancy for the entire study period and for up to 8 weeks after the last infusion.

2) Women who are pregnant or breastfeeding

3) Women with a positive pregnancy test on enrollment or prior to study drug administration

4) Males unwilling or unable to use an adequate method of contraception for the entire study period and for up to 8 weeks after the last infusion of study medication

Immunologic status

5) Subjects with PRA  $\ge$  30% at time of transplant

6) Subjects with zero HLA antigen mismatched donors (either from related or unrelated donor)

7) Subjects with any prior solid organ transplant (including kidney)

8) Subjects receiving a concurrent solid organ (heart, liver, pancreas) or cell (islet, bone marrow, stem cell) transplant

9) Subjects with a history of biopsy-proven acute rejection post-transplant (humoral or cellular) in the first three months post transplantation

Infection related risks

10) Subjects who are hepatitis C antibody-positive or polymerase chain reaction

(PCR)-positive for hepatitis C

11) Subjects who are hepatitis B surface antigen-positive or PCR-positive for hepatitis B

12) Subjects with known human immunodeficiency virus (HIV) infection

13) Subjects with active tuberculosis (TB) requiring treatment within the previous 3 years or any subject who previously required triple (or more) combination therapy for TB.

14) Subjects who are EBV antibody negative and have received grafts from EBV antibody positive donors.

Prohibited Therapies and/or Medications

15) Subjects who have used any investigational drug within 30 days prior to the Day 1 visit

16) Subjects previously treated with belatacept

18) Use of mTOR inhibitors at any time after transplantation

Other Exclusion Criteria

18) Prisoners or subjects who are compulsorily detained (involuntarily incarcerated) for treatment of either a psychiatric or physical (e.g., infectious disease) illness must not be enrolled into this study.

19) Subjects who have difficult i.v. access or other reasons that would likely preclude medication administration

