#### 6.4.2 Precautions

#### 6.4.2.1 Vaccinations

There is limited information available regarding the effectiveness of immunizations in non-human primates and humans that have been treated with belatacept. No data are available on the effect of therapeutic vaccinations in subjects receiving belatacept.

Due to the risk of infection, vaccination of subjects with any live vaccine is absolutely contraindicated during the course of the study, as is the administration of LIVE oral polio vaccine to household contacts. The Centers for Disease Control recommend that subjects should not be administered a live virus vaccination for at least 3 months after discontinuing high dose corticosteroid therapy (defined as > 20 mg/day of prednisone for > 2 weeks). In view of the long half-life of belatacept, study subjects should not be administered a live virus vaccine for a minimum of 3 months following the last dose of study medication.

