#### 7.2.4 Standard Study Visits

a) To occur on Weeks 4, 12, and 24 as well as week 48 for those electing to continue in the study

- b) Assess and record AEs pretreatment.
- c) Check and record any changes in concomitant medications
- d) Obtain weight and vital signs

e) Draw whole blood for immunology analysis, to be sent by courier to the Immunogenetics Center

- f) DSA testing
- g) EBV PCR testing

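### For men who complete dosing, the entry criteria end contraception at up to 8 weeks after the last infusion, 28 to 36 days plus 5 half-lives short of the period in Section 9.7

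*Combined protocol and SAP*

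**What the plan says.** The protocol states the duration of contraception for men in three places.

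- Section 5.1, item 6: "Men must use an adequate method of contraception throughout the study, and for up to 8 weeks after the last infusion".
- Section 5.2, item 4 excludes men who are unwilling or unable to use adequate "contraception for the entire study period and for up to 8 weeks after the last infusion of study medication".
- Section 9.7, Precautions, says men should be advised to "avoid unprotected sex throughout the study and until sperm produced during the period of drug exposure has been cleared". It then puts a time on this: "Drug-exposed sperm may be present in the semen for 3 months following the passage of 5 half lives of the study drug".

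The only pointer from the entry criteria to 9.7 is in Section 5.1, item 5, and it concerns women: "See section 9.7 below for details regarding handling of WOCBP subjects". Item 6, for men, has no pointer. No half-life in days appears anywhere. Section 6.4.2.1 has only a description: "In view of the long half-life of belatacept".

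**The concern.** The two entry criteria and the precaution address the same question, namely how long after the last infusion a man should avoid the risk of pregnancy in a partner. They give different answers, and the criteria give the shorter one. A man who completes dosing and meets items 6 and 4 exactly may stop contraception at a time when, on the protocol's own account, drug-exposed sperm may still be present. Staff who work from Section 5 have no pointer that would take them to the longer period for men.

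What is at stake is the safety of partners and of any pregnancy. The protocol treats this as a real matter: Section 9.7 asks for pregnancies in partners of male participants to be reported and for counseling to be offered. No endpoint, sample size or analysis depends on it.

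**Working it through.** **Inputs**

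- Period in the criteria after the last infusion: 8 weeks = 8 × 7 = 56 days (5.1 item 6, 5.2 item 4). The wording makes this a ceiling, so the gap below is a minimum.
- Period in 9.7 after the last infusion: 5 half-lives plus 3 months.
- Length of 3 months: Section 2.2 has "Donor specific antibody testing at Months 1 and 3", and Section 7.2.4 sets the matching visits "To occur on Weeks 4, 12, and 24 as well as week 48 for those electing to continue in the study". Month 3 is therefore week 12, or 84 days. In calendar terms 3 months is 89 to 92 days.
- Half-life: not stated.

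**Step 1. Gap when the 8-week limit governs**

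Gap = (3 months − 56 days) + 5 half-lives

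| 3 months taken as | Minus 56 days | Gap |
|---|---|---|
| 84 days (visit schedule) | 28 days (4.0 weeks) | 28 days + 5 half-lives |
| 89 days (shortest calendar) | 33 days (4.7 weeks) | 33 days + 5 half-lives |
| 92 days (longest calendar) | 36 days (5.1 weeks) | 36 days + 5 half-lives |

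The first term exceeds zero on every convention and the second cannot be negative, so the criteria are shorter whatever the half-life. As an illustration only, an assumed half-life of 5 days gives 53 to 61 days (28 + 25 to 36 + 25), and an assumed 14 days gives 98 to 106 days (28 + 70 to 36 + 70).

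**Step 2. For whom the 8-week limit governs**

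The criteria also run throughout the study, so they end at the later of study end and last infusion + 8 weeks. With study end at week 24, the 8-week limit governs if the last infusion is at week 24 − 8 = 16 or later. In the extension to week 48 the threshold is week 48 − 8 = 40.

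- Planned dosing ends at month 5 (Synopsis and 3.1.2; week 20) or month 6 (6.2.2, Belatacept Regimen; week 24). The criteria then end at week 28 or week 32. Both doses fall after week 16, so the full gap applies under either schedule.
- A man who stops drug and also leaves the study (6.6) has no further study period, so 8 weeks governs and the full gap applies to him too.
- A man who stops drug early but stays in follow-up to week 24, as 6.6 and 7.2.5 allow, is covered to week 24 (168 days). For a last infusion before week 16, his gap is last infusion + 84 to 92 days + 5 half-lives − 168 days, or zero if that is negative. For a last infusion at week 12 (84 days) this is 0 to 8 days + 5 half-lives. For week 4 (28 days) it is 5 half-lives minus 48 to 56 days, which may be nothing.

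**The case against.** The strongest reply is that the longer precaution is already in the protocol. Section 9.7 has no 8-week cap, Section 10.1 requires the study to be run as written, and a man can obey both texts at once. Section 5 sets conditions for entry. It is coherent for entry criteria to set a floor and for a precautions section to advise more. This stands in part: a reader might infer that men are left with no protection beyond 8 weeks, and the text does not support that. It does not remove the conflict, because the period a man must accept in order to enter is shorter than the one he is to be advised to follow, and nothing explains the difference.

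A second reply is that 9.7 says exposed sperm may be present, which is an outer limit on persistence. This stands. One might read 9.7 as giving the earliest date of clearance, or as saying that exposed sperm will be present after 8 weeks. It says neither.

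A third reply is that no harm is shown, and that what men are actually told is in the consent form, which was not available for this review. Both are true. The point is limited to a requirement that falls short of the protocol's own precaution.

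A fourth is that 8 weeks may have been chosen deliberately, so that 9.7 should be shortened instead. The protocol gives no rationale for 8 weeks in men, and nothing in it supports a shorter period in 9.7.

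**Conclusion.** The conflict is real. For men who complete planned dosing, or who leave the study when they stop drug, the required period is shorter than that in 9.7 by 28 to 36 days plus 5 half-lives. That the gap exists rests on the protocol's text alone; the 8-day spread comes only from how 3 months is counted. Its total length in days needs a half-life that the protocol does not give.

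The result does not extend to every man. For those who stop drug early and remain in follow-up, the gap is smaller or absent. Nor does it show a missing safeguard or any harm. It is an inconsistency on partner safety that should be corrected, with no bearing on the trial's endpoints or analysis.

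**What to change.** - In 5.1 item 6 and 5.2 item 4, change the duration to: throughout the study and for 5 half-lives plus 3 months after the last infusion. Express this in days, using the half-life in the product labeling.
- Add to item 6 a reference to the male precaution in 9.7.
- Check that the consent form gives men the same period.

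Align the duration only. Section 9.7 also restricts hormonal contraceptives, whereas 5.1 item 5 accepts one hormonal plus one barrier method, so adopting 9.7 as a whole would bring in a separate conflict.

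The cost is the wording of two criteria, one cross-reference and one check of the consent form. Visits, sample size and analysis do not change. The one downside is a longer contraception commitment for male participants.
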